9. RISKS

a. Potential Risks

i. Investigational devices

Anticipated Risks

Seizures

Repetitive transcranial magnetic stimulation is generally regarded as safe and without any serious or lasting adverse effects (Wasserman 1998; Rossi 2009). Inadvertent induction of a seizure is the most medically significant potential safety concern. However, there is no known risk of seizure for the above-stated brain stimulation parameters. The motor threshold is reflective of stimulation output necessary to cause neuronal depolarization. Since its first use in 2005, only one case of TBS has resulted in seizure, which occurred for stimulation at >100% resting MT (120% of aMT) and this was continuous TBS not iTBS. This proposed protocol involves iTBS delivered at 80% motor threshold. Finally, the proposed stimulation parameters mirror those used in Stanford IRB-approved iTBS protocols (Protocol Director [name]; ID 33797, ID 38138), which have received a “minimal risk” designation.

Studies evaluating the safety of iTBS in adolescents have shown it to be minimal risk (Hong et al., 2015; Wu et al., 2012).

Safety Monitoring for Potential Seizure Risk

Safety monitoring for the potential risk of seizure is addressed in several ways in this protocol. All subjects will be assessed during the screening phase for neurologic disease, concurrent medication use, or other clinical factors that may contribute to the risk of seizure. The Transcranial Magnetic Stimulation Adult Safety Screen (TASS) will be used as a screening tool to assure rigorous review of these clinical factors. Stimulation parameters have been selected to optimize the likelihood of clinical efficacy, while maintaining a safety level within the guidelines consistent with the 1998 NINDS workshop recommendations (Wasserman 1998).

All clinical personnel involved in the motor threshold determinations and the iTBS treatment sessions will be familiar with the ISTS Consensus Statement on Managing the Risks of Repetitive Transcranial Magnetic Stimulation, with specific attention to the requirements of medical supervision and first-responder capability in the event of a seizure as outlined in that document. Specifically, all personnel will be familiar with the procedures for subject screening for risk factors prior to treatment, individual risks and potential benefits for specific subjects, appropriate discussion of the risks and potential benefits of study participation as outlined in the informed consent document, the stimulation parameters to be used in this study, monitoring subjects for the potential development of seizures by continuous visual inspection during the course of each treatment session (especially the more subtle signs and symptoms of frontal lobe seizures), and first responder management in the event of a seizure. We will have immediate (i.e., within minutes) availability of more sophisticated medical support, including access to an emergency room, in the event that a seizure is not a self-limited

event, access to antiepileptic medications, and to life support equipment including oxygen, suction, blood pressure monitoring and cardiopulmonary (CPR) equipment.

As stated above, for all subjects who may experience a seizure during the study, the Investigator will provide a letter documenting that the seizure was experimentally produced.

If a seizure occurs during the study, that subject will be discontinued from the study.

ii. Investigational drugs

N/A

iii. Commercially available drugs, biologics, reagents or chemicals

N/A

iv. Procedures

Structural/Functional Head MRI

As this study only involves MR scans, the risk is assessed as minimal. No contrast material or exposure to ionizing radiation will occur for the conduct of this protocol.

To minimize any potential risks from the scans, the physician will ensure that the subject does not meet any contradictions for an MRI. Subjects who are uncomfortable in enclosed places (claustrophobic) may experience some discomfort. The MRI staff will be in contact with subjects at all times throughout the scanning process, and if necessary the scan can be stopped at any time. The total scanning time will be approximately 60 minutes per scanning session.

Participants may have tattoos or piercings that are magnetic. Because of the electromagnetic pulse, these might feel warm or hot during the treatment.

v. Radioisotopes/radiation-producing machines

N/A

vi. Physical well-being

The risks to physical well being include those listed above for study intervention (iTBS) and MRI.

vii. Psychological well-being

While completing the self report assessments and the clinical assessments, patients may become upset or frustration may occur.

Participants may not experience an improvement in mood or their mood may worsen over the course of the study.

Patients may find the study visits to be inconvenient.

viii. Economic well-being

The cost of patient's time for attending the study visits may be an economic difficulty.

ix. Social well-being

No risk to social well-being is anticipated.

x. Overall evaluation of risk

Medium

b. International Research Risk Procedures

N/A

c. Procedures to Minimize Risk

Management plan for treatment-emergent mania, exacerbation of depression, and/or suicidality

During the consent process, subjects and families will be educated about the possibility of significant changes in mood, suicidal thinking, and/or behaviors during the treatment. These changes could include emergence of mania, worsening of depression, and/or suicidal thinking and behaviors. Both the subject and parent(s) will be told to initiate contact with their study doctor, if they experience any significant mood or behavior changes including suicidal ideation. Principal Investigator contact information is included in the consent/assent document. Furthermore, during the protocol, subjects will have assessments weekly where changes of psychological symptoms will be queried. Ongoing monitoring for worsening of depression and emergence of suicidal ideation and/or behaviors will be evaluated using the HAMD, C-SSRS, and CGI-S.

Suspected treatment-induced mania will be evaluated using the Young Mania Rating Scale (YMRS). A YMRS score of ≥ 20 will prompt administration of the M.I.N.I./M.I.N.I. KID to determine whether or not the subject meets the Diagnostic and Statistical Manual of Mental Disorders, Fifth Edition (DSM-5) criteria for mania. A YMRS score of 20 or greater will be considered an adverse event (AE) and will be monitored using the YMRS; the emergence of DSM-5 verified mania will be treated as a serious adverse event (SAE) and will also be monitored using the YMRS.

Exacerbation of depression, suicidality or induction of mania would constitute an SAE and the subject would be discontinued from the study. Subject would then be referred for clinical follow-up outside of the study.

Treatment plan for other side effects of iTBS experienced during treatment:
Repositioning of coil and prophylactic use of acetaminophen or ibuprofen will be allowed for subjects reporting sensations at or near the stimulation site which are uncomfortable or painful. During the first week of treatment only.

Treatment plan for other potential side effects experienced following treatment:

Subjects reporting headaches during or following study treatment will be encouraged to take acetaminophen or ibuprofen prior to the daily treatment. To reduce the risk of temporary or permanent hearing loss due to noise emitted from the stimulator, subjects will wear protective ear plugs during treatment. All subjects will be monitored, and appropriate treatment will be recommended including the possibility of stopping iTBS. Any other potential side effects will be managed symptomatically with treatment(s) deemed appropriate by the study site Principal Investigator. All symptomatic interventions will be recorded in the subject's case file and, if applicable, adverse event CRF.

d. Study Conclusion

Subjects may withdraw voluntarily from the study at any time. They may be withdrawn from the study by the Investigator if a subject:

- experiences a seizure,
- experiences a DSM-5-confirmed treatment-induced mania,
- is non-compliant with study procedures

The Investigator may also withdraw a subject if he/she believes that for safety reasons it is in the best interest of the subject to be withdrawn.

Discontinuation information [e.g., date and the reason(s) for discontinuation] must be recorded in the subject's CRF (i.e., Study Completion Form). Subjects who discontinue prematurely should complete the final assessments within 2 days following their last iTBS treatment session.

Subjects withdrawn from the study due to an AE will be followed up for 30 days or until resolution.

e. Data Safety Monitoring Plan (DSMC)

i. Data and/or events subject to review

The IRB has oversight for the overall safety of the study. Safety monitoring will include careful assessment and appropriate reporting of adverse events as noted above, as well as the construction and implementation of a data and safety-monitoring plan. Medical monitoring will include a regular assessment of the number and type of serious adverse events.

ii. Person(s) responsible for Data and Safety Monitoring

The protocol director will be responsible for data and safety monitoring for this pilot study.

iii. Safety Reporting

Any SAE, regardless of causal relationship, will be reported immediately to the IRB (within one business day). Compliance with this time requirement is essential so that the IRB may comply with its regulatory obligations.

Follow-up information relating to an SAE must be reported to the IRB after the information is received by the Investigator by faxing a completed serious adverse event form to the fax telephone number listed in Section 1.2 of this protocol and confirming by telephone that the fax was received. The subject should be observed and monitored carefully until the condition resolves or stabilizes or its cause is identified.

iv. Specific triggers or stopping rules

Specific occasions when study treatment may be stopped are explained Section 8.4 in the discussion of Anticipated Risks.

Because of the anticipated low level of adverse events of iTBS, the PD will be charged with reviewing adverse events at least every six months. Serious adverse events will be reviewed on a monthly basis, unless a more urgent review is requested.

v. DSMB Reporting

The outcome of the review will be disseminated to the investigators as appropriate.

vi. Will a board, committee, or safety monitor be responsible for study monitoring?

Yes

f. Risks to Special Populations

iTBS may be a beneficial treatment for adolescents that have not responded well to medication. The risks of iTBS are less great than alternative approaches such as ECT.

All parents or LAR will sign consent for adolescents bw 12-17 yo inclusive. All adolescents bw 12-17yo will also sign assent. These consent and assent procedures are applicable for both the parent and the MRI portion of the study.

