2. STUDY PROCEDURES

a. Procedures

Screening

Subjects will undergo medical, psychological and neuropsychological assessments to assure compliance with all inclusion and exclusion criteria. Eligible subjects will receive active iTBS.

TMS Treatment

All treatments and motor threshold determinations will be completed by physicians or other health care providers who have been trained to the process based on the MagVenture User Manual and certified by the department. All processes are consistent with the clinical use of the MagVenture MagPro rTMS research system.

iTBS sessions will occur approximately 2 days after the baseline session with week daily sessions delivered to left DLPFC over 6 weeks. We will start with the currently FDA approved iTBS protocol for adults. Stimulation will be administered using the MagVenture MagPro rTMS Research System at currently FDA approved parameters: 80% of the active motor threshold, 20 cycles of 10 bursts of 3 pulses at 50Hz delivered in 2 second trains with an 8 second inter-train interval. The stimulation will be applied for

3 min delivering a total of 1800 pulses/session. These stimulation sessions will occur daily (week days) for 6 weeks. Resulting in a total of 30 sessions. Motor Threshold (MT) Determination: MT Location and MT Level - The motor threshold location will be determined by visual confirmation of the location on the motor cortex that controls the abductor pollicis brevis (APB) muscle of the thumb. The resting MT level is the minimum power to produce a stimulation response 50% of the time.

Prophylactic use of acetaminophen or ibuprofen will be allowed for subjects reporting sensations at or near the stimulation site which are uncomfortable or painful. During the first week of treatment only, in the event that the subject cannot tolerate the treatment at these dose parameters, dose intensity may be titrated downward to 110% of the motor threshold, with all other dose parameters remaining the same.

Heart Rate Variability (HRV)

Participants will have their HRV measured before they receive any stimulation, at the end of each stimulation week and at the end of the six week treatment course. HRV will be measured using ECG electrodes attached to the wrists and an r-wave trigger device (neuroConn, Ilmenau, Germany). HRV will be measured when viewing videos depicting negative emotions (e.g. anger, fear) and when viewing neutral stimuli.

Structural/Functional Brain MRI

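### Sections 2.a and 9.c disagree on when analgesics may be used for stimulation-site discomfort, so the rule for weeks 2 to 6 is unclear

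*Combined protocol and SAP*

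**What the plan says.** Section 2.a (Procedures, TMS Treatment) sets the course: "week daily sessions delivered to left DLPFC over 6 weeks", given on weekdays, "Resulting in a total of 30 sessions". On tolerability it makes two separate statements. The first is "Prophylactic use of acetaminophen or ibuprofen will be allowed for subjects reporting sensations at or near the stimulation site", with no limit of time. The second opens a new sentence: "During the first week of treatment only, in the event that the subject cannot tolerate the treatment at these dose parameters". That sentence goes on to allow the intensity to be lowered to 110% of the motor threshold. The first-week limit therefore belongs to the intensity change.

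Section 9.c (Procedures to Minimize Risk, side effects during treatment) says "Repositioning of coil and prophylactic use of acetaminophen or ibuprofen will be allowed for subjects reporting sensations at or near the stimulation site". The intensity change is absent. The paragraph ends with the first-week words standing alone: "which are uncomfortable or painful. During the first week of treatment only". The next paragraph, on side effects after treatment, says that subjects with headache during or after treatment will be "encouraged to take acetaminophen or ibuprofen prior to the daily treatment", with no week limit.

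**The concern.** The same limiting phrase governs different measures in the two sections. Suppose a subject reports pain under the coil in week 3. Staff using Section 2.a would find an analgesic allowed. Staff using Section 9.c, as printed, would find that the period for it had ended. If the complaint were recorded as headache, Section 9.c would encourage the same drug.

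What is at stake is consistent handling of participants aged 12 to 21, all of whom receive active stimulation, and a risk section that matches the procedures section. The choice of measure may affect who tolerates the course and at what exposure, but the documents give no basis for putting a size on that.

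**Working it through.** This is a comparison of text. The only arithmetic concerns the share of the course affected and the intensity figures.

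**Schedule.** Section 2.a gives weekday sessions for 6 weeks: 6 × 5 = 30, which reproduces its stated total. Week 1 holds 5 sessions. Weeks 2 to 6 hold 5 × 5 = 25, and 25/30 = 83%.

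**The sections side by side, as printed.**

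| Measure | Section 2.a | Section 9.c | Result |
|---|---|---|---|
| Analgesic for site discomfort | Allowed, no limit | Allowed, followed by the first-week fragment | Conflict in weeks 2 to 6 |
| Coil repositioning | Not mentioned | Allowed, followed by the first-week fragment | Stated once; no conflict |
| Lower intensity | Week 1 only | Not mentioned | Stated once; missing from 9.c |
| Analgesic for headache | Not mentioned | Encouraged, no limit | A different complaint; no conflict in itself |

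Only the first row is both allowed and, on a literal reading, not allowed.

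**Two readings of the fragment.**

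1. It is a limit on what precedes it. Analgesics and repositioning then end after week 1 under 9.c, against the open-ended permission in 2.a. Whether a subject may take the drug in weeks 2 to 6 also depends on whether the complaint is called site pain or headache.
2. It is the opening of the 2.a intensity sentence with the remainder lost. The two sections then agree on analgesics, but 9.c has dropped a dose modification that 2.a permits, and repositioning has no stated period.

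Reading 1 is a contradiction and reading 2 an omission. Nothing on the page settles which was intended.

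**The intensity sentence.** Section 2.a sets stimulation at 80% of the active motor threshold, and Section 9.a repeats 80% of motor threshold. The tolerability step goes downward to 110% of the motor threshold. On a common threshold, 110% is higher than 80%, so the step is not a reduction. Section 2.a does not say which threshold the 110% refers to, and the level it defines is the resting one. For 110% of another threshold to equal 80% of the active one, that threshold would have to be 0.80/1.10 = 0.73 of the active threshold; for a reduction, it would have to be lower still. The documents state no such relation. Copying this sentence into a merged rule would therefore carry a second inconsistency with it.

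**The case against.** The strongest reply is that the fragment has no verb, matches the opening of the 2.a intensity sentence word for word, and follows the same analgesic sentence. A copying error is at least as plausible as a deliberate limit. This stands, and it means that Section 9.c cannot be said to intend a ban. It does not remove the need to repair the text, because a truncated rule in the risk section is itself a defect.

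Several stronger readings are tempting and are not supported:

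- *Subjects have no relief for site pain in most of the course.* Section 2.a still allows analgesics. Section 9.c also lets the investigator manage other side effects symptomatically. That discretion stands under the heading for effects after treatment, so it softens the literal reading without resolving it.
- *A repositioned coil may leave the target.* Section 2.a fixes the target as left DLPFC and requires trained, certified staff. Section 9.c permits repositioning, not a new target. How far the coil may move is missing detail, not a contradiction.
- *Modified sessions go unrecorded, or count as per-protocol.* Section 9.c has all symptomatic interventions entered in the case file, and the protocol defines no per-protocol set.
- *The earlier adolescent study predicts drop-out.* In Section 3.a, 1 of 8 subjects left after 5 minutes of treatment, citing scalp discomfort and a perceived lack of improvement. That says nothing about weeks 2 to 6 and cannot be projected onto this study.
- *Sites will diverge, or the result will change.* Section 8.a plans all 30 subjects at one institution, and no effect on the result is shown.

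**Conclusion.** The point holds in a limited form. Sections 2.a and 9.c conflict on when analgesic prophylaxis for site discomfort is allowed or, if the fragment is a truncated copy, Section 9.c is incomplete. Either way the operating rule for weeks 2 to 6 cannot be read from the protocol with confidence.

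The 25 of 30 sessions is an upper bound on reach: only sessions in which a subject has site discomfort are affected, and the documents do not say how often that is. The figure assumes the planned weekday schedule is delivered in full. The matter is one of consistent conduct. It changes no sample size, power or error rate.

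**What to change.** Reconcile Sections 2.a and 9.c into one tolerability rule, placed in one section with the other referring to it. For each measure already named (analgesic, coil repositioning, intensity change), state the weeks in which it applies. Make clear how the site-discomfort rule and the headache rule relate, since both concern the same drugs. In the same pass, reconcile the step downward to 110% with the stated 80%, including which motor threshold each percentage refers to. The content of each rule is for the sponsor and investigator to decide.

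The cost is amendment wording. No visit, assessment or analysis changes as a result of the reconciliation itself.

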patient is as follows: The investigators for this project are not trained to perform radiological diagnosis, and the scans performed in this study are not optimized to find abnormalities. The investigators and Stanford are not responsible for failure to find existing abnormalities in your MRI scans. However, on occasion the investigator may notice a finding on a MRI scan that seems abnormal. When this occurs, a radiologist will be consulted as to whether the finding merits further investigation, in which case the principal investigator of the research study being conducted will contact the participant's primary care physician and inform them of the finding. The decision as to whether to proceed with further examination or treatment lies solely with the participant and his/her physician. The investigators, the consulting radiologist, and Stanford are not responsible for any examination or treatment that you undertake based upon these findings. Because the images collected in this study do not comprise a proper clinical MRI series, these images will not be made available for diagnostic purposes. In the event that a potential abnormality on the MRI images is detected by the researchers, the magnet manager, is to be notified immediately to report the potential issue. Films of images are not be provided to the researcher or volunteer scan subject as the images were obtained using a research MRI scan protocol and not from a clinically- ordered MRI scan protocol prescribed by a radiologist at Stanford.

b. Procedures to Minimize Risks

Outcome Assessments

Trained physicians and raters will administer all diagnostic assessments and clinical interviews determining study eligibility during screening. All study staff will be trained on study procedures.

Outcome screening will occur after both the Informed Assent/Consent Document and the HIPAA Authorization are signed. Baseline assessments will occur prior to the first iTBS treatment session.

The following outcome assessments will be completed: HAMD/MADRS structured interview, CDRS-R, CGI-S, and QIDS-A17-SR.

Safety Assessments

A physical and complete medical and psychiatric history will be obtained at the screening visit. Subjects will be evaluated clinically for adverse events at each visit. SAEs will be recorded as they occur and reported to the IRB within one business day of notification.

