Efficacy of TMS for the treatment of adolescent depression, for all TMS devices including the NeuroStar TMS Therapy® System, has been reported in two pilot clinical studies and in multiple case reports (Walter 2001; Bloch 2008; Wall 2011). These open-

label studies describe the treatment of 24 patients, ages 10-18. The 2011 Wall et al. open-label trial is the only study that used the NeuroStar TMS Therapy System. This study reported on the treatment of 7 antidepressant-resistant adolescents and demonstrated a robust response rate noted by 5 of 7 subjects achieving remission of depression, as rated using the Childhood Depression Rating Scale – Revised (CDRS-R). Furthermore, CDRS-R mean depression severity scores were significant by treatment 20 as compared to baseline with similar efficacy demonstrated using the patient reported Quick Inventory of Depressive Symptoms – Adolescent Version (QIDS-A17- SR). Placebo effects in open-label trials of adolescents are a well-known phenomenon. However, adolescents demonstrate enduring mood improvement for at least 6 months following their final acute treatment (session 30). Furthermore, 7 of 8 subjects completed the entire treatment course, with 1 patient exiting the study after only 5 minutes of treatment due to scalp discomfort and a perceived lack of improvement.

iTBS has been shown to be more effective at inducing antidepressant responses in adults than traditional rTMS. 3 minutes of iTBS induce equivalent antidepressant responses as 37 minutes of traditional rTMS stimulation (Blumberger et al., 2015) and lower stimulation intensities are required to induce antidepressant responses (Wu, Shahana, Huddleston, Lewis, & Gilbert, 2012).

The shorter stimulation times and the lower stimulation intensities required for iTBS in comparison to traditional rTMS make iTBS potentially advantageous method for adolescents with MDD. Traditional rTMS has been shown to be effective at reducing depressive symptoms in adolescents (Carpenter et al., 2012) but iTBS has not been trialled in adolescents with MDD. Initial trials investigating the safety of iTBS in adolescents have identified iTBS as minimal risk (Hong et al., 2015; Wu et al., 2012).

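### Non-serious adverse events need a pooled review only every six months although a course lasts six weeks; about 6 to 8 of 30 participants could finish before the first one

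*Combined protocol and SAP*

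**What the plan says.** Section 9.e.iv sets two review frequencies. For adverse events in general, "the PD will be charged with reviewing adverse events at least every six months"; the reason given is that few adverse events are expected. For serious events the next sentence is stricter: "Serious adverse events will be reviewed on a monthly basis, unless a more urgent review is requested". Section 9.e.i describes medical monitoring as a regular assessment of serious events only. Section 9.e.ii makes the protocol director responsible for data and safety monitoring.

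Three other provisions bear on the point.

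- **Individual checks.** Section 2.b (Safety Assessments): "Subjects will be evaluated clinically for adverse events at each visit". Section 9.c adds that "subjects will have assessments weekly where changes of psychological symptoms will be queried".
- **What counts as serious.** Section 9.c: "Exacerbation of depression, suicidality or induction of mania would constitute an SAE and the subject would be discontinued from the study". Serious events also go to the IRB within one business day (9.e.iii).
- **What stays non-serious.** Under Section 9.c a YMRS score of 20 or more is an adverse event, and mania becomes a serious one when verified against DSM-5. Section 9.c also anticipates discomfort at the stimulation site and headache, and gives management steps for them without classing them as serious.

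A course is six weeks of weekday sessions (2.a), and 30 participants are planned (8.a).

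**The concern.** The minimum review interval is long compared with the time a participant is exposed. Visit-level checks serve the individual in front of the assessor. A pattern across participants, such as several raised YMRS scores or repeated intolerance of stimulation, is something that only a review across participants is designed to show. For non-serious events the plan requires that review so rarely that some participants could start and finish treatment before it first takes place.

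The population makes this worth a look. Section 3.a says that "iTBS has not been trialled in adolescents with MDD", Section 8.c says that safety in adolescents is under investigation, and Section 9.a.x rates the overall risk as medium. Section 3.a also reports an open-label adolescent trial of conventional TMS in which 1 of 8 participants left after five minutes, partly because of scalp discomfort. Tolerability signals are therefore plausible here without reaching the level of a serious event.

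At stake is how early such a signal is recognised, not whether individuals are monitored.

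**Working it through.** The protocol states no accrual rate and no share of participants treated before the first review, so there is no figure of its own to reproduce. The size below rests on an assumed accrual pattern.

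**Inputs**

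- Maximum interval between required adverse event reviews: 6 months (9.e.iv).
- Course length: 6 weeks (2.a), so c = 42 / 30.4375 = 1.38 months.
- Sample size: 30 (8.a).
- Study duration T: two years (8.m), or spring 2019 to the end of 2020 (2.g). A start at the beginning of March gives 22 months and at the beginning of June 19 months. The range used is 19 to 24 months.

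**Assumptions**

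Uniform accrual, no dropout, and a review clock that starts at first enrolment.

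**Interval in courses**

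6 / 1.38 = 4.3 courses per review interval.

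**Share finished by month 6**

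To have finished by month 6, a participant must have started by month 6 − 1.38 = 4.62. Two accrual windows are reasonable:

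- A: the last participant finishes at T, so accrual lasts T − c. Share = 4.62 / (T − 1.38).
- B: accrual is spread over all of T. Share = 4.62 / T.

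The last column gives those merely enrolled by month 6, as 6 / T, for comparison.

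| T (months) | Finished, A | Finished, B | Enrolled, 6 / T |
|---|---|---|---|
| 19 | 26.2% (7.9 of 30) | 24.3% (7.3) | 31.6% (9.5) |
| 20 | 24.8% (7.4) | 23.1% (6.9) | 30.0% (9.0) |
| 21 | 23.5% (7.1) | 22.0% (6.6) | 28.6% (8.6) |
| 22 | 22.4% (6.7) | 21.0% (6.3) | 27.3% (8.2) |
| 24 | 20.4% (6.1) | 19.3% (5.8) | 25.0% (7.5) |

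The finished share therefore runs from 19% to 26%, about 6 to 8 of 30. Under A it passes 25% only if T is below 1.38 + 4.62 / 0.25 = 19.9 months. Under B it stays below 25% throughout the range.

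**With a monthly review**

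One month is shorter than the 1.38-month course, so nobody can complete a course before the first review (0 of 30).

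**Number on treatment at once**

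At T = 21, accrual is 30 / 21 = 1.43 a month, and 1.43 × 1.38 = 2.0 participants are on treatment at any time. The range is 1.7 (T = 24, 1.25 a month) to 2.2 (T = 19, 1.58 a month).

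**The case against.** The case for leaving the interval alone is substantial.

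- **The gravest events are outside the gap.** Exacerbation of depression, suicidality and induced mania are serious events by definition in Section 9.c. They are reviewed monthly and go to the IRB within a business day. This stands, and it limits the point to non-serious events.
- **Each remaining signal has an individual response.** A YMRS score of 20 or more prompts a structured diagnostic interview and continued YMRS monitoring, and discomfort has its own management steps. This stands for the individual, but it is not a review across participants.
- **The trial is small.** With about two participants on treatment at once at a single site, the same staff may notice a pattern informally, and each monthly listing would add little. Most participants (1 − 6/T, or 68% to 75%) have not yet enrolled at month 6 and would benefit even from a six-monthly review. This stands, and it makes the gain modest.
- **Six months is a floor.** The protocol director may review sooner. That is true, but nothing requires it.
- **The low expectation has a stated basis.** A reader might infer that the absence of earlier iTBS trials in adolescents with MDD contradicts it. The documents do not support that. The sentence appears in a comparison with the efficacy of conventional rTMS, and the next sentence reports that initial safety trials of iTBS in adolescents found minimal risk. Section 9.a repeats this, and Section 3.a also describes rTMS and iTBS as well tolerated in pediatric populations.

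The documents cite no standard that a six-month interval would breach, and they do not contradict themselves on it.

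**Conclusion.** The point holds as a minor, inexpensive improvement. Non-serious adverse events have no required pooled review for up to six months, about 4.3 courses. On uniform accrual over 19 to 24 months, about 6 to 8 of 30 participants (19% to 26%) could finish before the first such review. The figure depends on the accrual assumption: faster early recruitment would raise it, and slower early recruitment would lower it.

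Two stronger readings are not supported. A reader might infer that these participants finish before any required safety review; the monthly review of serious events and the checks at each visit rule that out. A reader might also put the share above a quarter by taking 30 / 21 × 6 = 8.6 of 30 (29%). That counts participants enrolled by month 6, some of whom are still on treatment. On the stated two-year duration the finished share is about one fifth.

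**What to change.** In Section 9.e.iv, replace the six-month minimum with a monthly minimum, and state that the protocol director reviews a pooled listing of all adverse events, serious and non-serious, at the monthly serious-event review already planned. The existing provision for a more urgent review can stay as it is.

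The cost is a small amount of listing work each month, with no added staff, visits or participants. The change concerns the timing of oversight only and leaves treatment and individual management untouched.
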